13.1.2. Interval Based Cox Proportional Analysis for Fabry-associated Clinical Events

In the interval-based time to event analysis will be used with 3 time-dependent variables indicating whether or not a patient is on migalastat, ERT, or untreated at time t . A patient may be in 1 or more treatment groups and a patient may be both left and right censored. For example, a patient that begins migalastat, stops at Month 9, begins ERT at Month 24, and then dies at Month 26 will be represented 3 times in the design matrix; the first for migalastat being right censored at Month 9, the second being for ERT left censored at Month 24 and right censored at Month 26, and finally, for untreated, being right censored at Month 9 and having an event at Month 24.

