3. STUDY ENDPOINTS

3.1. Primary Effectiveness Analysis

The primary endpoint is time to first FACE (cardiac, renal, or cerebrovascular events) ") since start of treatment for migalastat and or ERT and from time of diagnosis for untreated with particular focus on the added value of the recent addition of migalastat as a treatment option. A formal statistical analysis will be using the initial treatment cohort. Descriptive statistics will be calculated since each start of treatment (after each switch).

FACEs are defined as the following:

- Cardiac clinical events:
 - Myocardial infarction
 - New symptomatic arrhythmia requiring medication, direct current cardioversion, or interventional procedure (e.g., ablation, pacemaker, or defibrillator implantation)
 - Unstable angina defined by national practice guidelines and accompanied by electrocardiographic changes and non-ST segment elevation myocardial infarction [UA/NSTEMI]) and accompanied by electrocardiographic changes
 - Congestive heart failure requiring hospitalization
 - Any major cardiac medical procedure (e.g., valve replacement, stent-implantation, transplant, or persistent atrial fibrillation)
- Cerebrovascular clinical events:
 - Stroke (documented by a physician)
 - Transient ischemic attack (documented by a physician)
- Renal clinical events
 - Doubling of serum creatinine level from the start of analysis (2 consecutive values)
 - End-stage renal disease (ESRD) requiring long-term dialysis or transplantation
- Death due to FACEs

All FACEs will be analyzed together as a composite and separately in each category (cardiac, cerebrovascular, and renal). Death due to FACE will be analyzed under the category in which it occurred (cardiac, cerebrovascular, or renal).

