3.2. Secondary Effectiveness Analysis

Secondary endpoints listed below will be assessed by evaluating migalastat-treated and untreated patients and/or migalastat-treated and ERT-treated patients:

- The prevalence of FACEs from each baseline (diagnosis, and start of treatment) in migalastat-treated, ERT-treated patients and untreated patients

- The incidence of FACEs from each baseline (diagnosis, and start of treatment in migalastat-treated, ERT-treated patients and untreated patients
- Time to the first cardiac, cerebrovascular, and renal clinical event separately by each specific category (including death in these categories) from baseline (diagnosis and start of each treatment) using Cox proportional hazards model and descriptive statistics.
- Incidence of cardiac, cerebrovascular, and renal clinical events separately by each specific category (including death in these categories)
- Occurrence of cardiac, cerebrovascular, and renal clinical events separately by each specific category (including death in these categories)
- Annualized rate of change in eGFR based on the Chronic Kidney Disease Epidemiology Collaboration equation (eGFR CKD-EPI) over time in migalastat-treated, ERT, and untreated patients . Analysis will also be performed by eGFR category at baseline if the counts are sufficient.
- The prevalence and incidence of a clinically significant change in mGFR and/or eGFR (according to KDIGO guidelines rapid progression is defined as a sustained decline in eGFR of more than 5 ml/min/1.73 m²/yr) from each baseline (diagnosis, and start of treatment) in migalastat-treated, ERT-treated patients and untreated patients.
- The prevalence and incidence of micro (> 30 mg/g creatinine) or macroalbuminuria (> 300) by urinary albumin/creatinine ratio (ACR) or urinary 24 h protein excretion from each baseline (diagnosis, and start of treatment) in migalastat-treated, ERT-treated patients and untreated patients.

The analysis for the primary effectiveness endpoint will be performed at the 2-sided significance level of 0.05 to compare migalastat-treated and untreated patients. All other comparisons will also be done at the 2-sided significance level of 0.05 with no adjustment for multiple comparisons.

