13.1.1. Cox Proportional Analysis for Fabry-associated Clinical Events

The time to the first event is defined as time from the Analysis Start Date to the first composite FACE (primary interest), and to the first cardiac, cerebrovascular, renal clinical event, or death due to FACEs. For the primary analysis, patients who complete the study without an event, are lost to follow-up, discontinued the study, started dialysis, had a kidney or heart transplant, or after 30 days they changed/switched therapy (migalastat group) or after they start therapy (untreated group) will be censored. Describing effectiveness in migalastat treated population is of the main interest.

Treatment Switch

The primary analysis will address events that occur on therapy from the Analysis Start Date up until 30 days after the patient stops therapy or switches therapy. The events that happen afterwards will be excluded. For the patients untreated at time of diagnosis, the primary analysis will address events from the time of diagnosis until the patient starts a therapy. The events that happen afterwards will be excluded. An additional analysis will be performed:

1. An analysis that will address events that occur on therapy from the time of Analysis Start Date up until the patient stops therapy or patient switches therapy. For the untreated patients, the analysis will address assessments from the time of diagnosis until the patient starts a therapy. The events that happen afterwards will be excluded.

Primary Analysis Method

The ratio of the hazards of treatment groups will be checked to ensure that the hazard ratios are constant over time. Secondly, the assumption that each variable in the model makes a linear contribution will be checked.

The covariates will include:

- sex
- age at the Analysis Start Date as a continuous variable
- eGFR_{CKD-EPI} at the Analysis Start Date as a continuous variable
- LVMi at the Analysis Start Date
- previous history of cardiac, cerebrovascular, and renal clinical events (composite event) as related to Analysis Start Date
- Length of treatment for Fabry disease

If the measurements are not available, measurements prior to and closest to the Analysis Start Date will be used. In case that more than 50% of values are missing for a given covariate, it will be dropped from the analysis.

The estimate of hazard ratio for migalastat-treated/untreated along with the associated 95% CI will be calculated.

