A sensitivity analyses will be done using Kaplan-Meier approach (log-rank test).

The analysis between migalastat and ERT will be performed like the analysis above for the comparison between migalastat treated and untreated patients. The origination of analysis will be start of treatment.

Because patients could switch treatment many times during the 20-year period, the time to the first event within each treatment period will be calculated from each switch date and descriptive statistics will be presented. Please note that each patient could be counted more than once in this analysis. Two options will be used for these analyses. The first analysis will address events that occur on therapy from the Analysis Start Date up until 30 days after the patient stops therapy or from the switch date to the date of a subsequent switch or stopping therapy. The second analysis will address events that occur on therapy from the Analysis Start Date up until the patient stops therapy or switches therapy or from the switch date to the date of a subsequent switch or stopping therapy.

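### SAP 13.1.2 names no covariates for the interval-based Cox model, so a hazard ratio against untreated time is open to confounding by disease stage at drug start

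*SAP*

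**What the plan says.** SAP 13.1.2 describes a Cox model with "3 time-dependent variables indicating whether or not a patient is on migalastat, ERT, or untreated" at time t. It then gives a worked example of how one patient is split into rows. It names no other model term, no reference category and no hazard ratio to be reported.

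The neighbouring section, 13.1.1, does list model terms under its primary analysis method: "The covariates will include" sex, age, eGFR, LVMi, FACE history and length of treatment. Age, eGFR and LVMi are taken at the Analysis Start Date, and history is worded as "previous history of cardiac, cerebrovascular, and renal clinical events (composite event) as related to Analysis Start Date". SAP 11.2 sets that date at diagnosis for migalastat against untreated, and at treatment start for migalastat against ERT.

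On time after a switch, SAP 3.1 says "A formal statistical analysis will be using the initial treatment cohort". For later periods, 13.1.1 says "the time to the first event within each treatment period will be calculated from each switch date and descriptive statistics will be presented". Two other passages touch on the same time:

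- SAP 3.2 plans category-specific analyses "from baseline (diagnosis and start of each treatment) using Cox proportional hazards model and descriptive statistics".
- For migalastat against ERT, 13.1.1 says "The origination of analysis will be start of treatment".

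SAP 15.4 models overall survival in a similar way to 13.1.2. A covariate list stands earlier in 15.4, but the text does not say whether it applies to the time-dependent model.

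**The concern.** All patients are treatment-naïve at diagnosis (SAP 2). Follow-up starts in 2001, while migalastat has been available only since 2016 (protocol, Rationale and background). A patient enrolled untreated counts as initially treated only if a drug is started within 3 months (SAP 5.2.1). Much migalastat time may therefore be reached after ERT or after untreated years. For the composite FACE against untreated, that time enters a model through 13.1.2.

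A programmer following 13.1.2 literally would fit treatment indicators alone. That sets later on-drug time against earlier untreated time with no account of disease state when the drug was started. If drugs are started as organ function declines, the decline is charged to the drug. The study's stated focus is migalastat, so a distorted hazard ratio here would matter even though the model is not the primary one.

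**Working it through.** **1. Adjustment, section by section.** SAP 13.1.1, 13.7 and 15.4 each list covariates and a rule for missing values. SAP 13.1.2 has neither, and no cross-reference to a list. If the 13.1.1 list is carried over for migalastat against untreated, age, eGFR, LVMi and FACE history are those at diagnosis, however much later the drug was started.

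**2. The model.** With M(t), E(t) and U(t) marking migalastat, ERT and untreated, M + E + U = 1 at every time, so one must be the reference. With untreated as reference and nothing else in the model:

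hazard(t) = h0(t) × exp[βM·M(t) + βE·E(t)]

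Suppose the drug does nothing and a progressed state multiplies the FACE hazard by b. The hazard ratio this model sees at time t is

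[1 + (b − 1)·p_on(t)] / [1 + (b − 1)·p_un(t)]

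where p_on and p_un are the progressed fractions among those at risk on drug and untreated. It equals 1 when the fractions are equal and exceeds 1 when progressed patients start treatment sooner.

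**3. Size.** The documents give no event count, FACE rate or starting rate, and no hazard ratio for this model, so there is no figure to reproduce. Two simulations with different assumptions were run, both with a true hazard ratio of 1.

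*Simulation A.* 115 patients, 4 to 20 years of follow-up, and one severity score raising both treatment start and FACE hazard by 1.5 to 2 times per SD. There were 30 to 36 events and 400 cohorts for each of three scenarios.

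| | Scenario 1 | Scenario 2 | Scenario 3 |
|---|---|---|---|
| Median HR, indicators only | 1.23 | 1.38 | 1.71 |
| Rejection at 5% | 0.05 | 0.13 | 0.31 |
| Median HR, severity at interval start | 0.98 | 0.96 | 0.98 |

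Rejection after adjustment was 0.04 to 0.05.

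*Simulation B.* A binary progression state multiplies the FACE hazard by b and the drug-start rate by g. Assumed rates per year: FACE 0.02, drug start 0.06, progression 0.05. Follow-up is 2 to 22 years, migalastat is available for the last 6.5, and switching from ERT to migalastat is unrelated to progression. Ten runs of 4000 patients per setting gave these migalastat/untreated hazard ratios:

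| g, b | Indicators only | Plus baseline covariate | Plus time-updated state |
|---|---|---|---|
| 1, 3 | 1.01 | 1.01 | 1.03 |
| 2, 2 | 1.20 | 1.17 | 1.08 |
| 2, 3 | 1.16 | 1.14 | 1.00 |
| 4, 2 | 1.28 | 1.22 | 1.01 |
| 4, 3 | 1.40 | 1.34 | 1.01 |
| 8, 3 | 1.73 | 1.63 | 1.06 |

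The Monte Carlo standard error is 0.02 to 0.05 on the log scale. Where g exceeds 1, the baseline covariate removes only 12.5% (0.02/0.16) to 21% (0.06/0.28) of the excess over 1. The time-updated state removes most or all of it.

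At 115 patients (31 to 35 events), the median indicator-only hazard ratio in B was 1.05 (g = 2, b = 2) to 1.36 (g = 4, b = 3). The false-positive rate was 5.0% to 7.8%, from 378 and 386 usable runs of 400. Migalastat against ERT stayed at 0.98 to 1.08 in the large samples.

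**4. The worked example.** The patient takes migalastat to Month 9, starts ERT at Month 24 and dies at Month 26.

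| State | Rows that follow from the story | Rows as printed in 13.1.2 |
|---|---|---|
| Migalastat | 0 to 9, no event | censored at 9 |
| Untreated | 9 to 24, no event | censored at 9, event at 24 |
| ERT | 24 to 26, event | 24 to 26, censored |

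The death on ERT is moved to untreated time. If every patient were coded this way, simulation B gives a drug/untreated hazard ratio of about 0.03 to 0.05 when the truth is 1. The example in 15.4 also disagrees with its own story: ERT starts at Month 6 and death follows at Month 9, yet the rows place ERT at Months 3 to 6 and the event in the untreated row.

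**The case against.** The strongest reply is that 13.1.2 never says the model is unadjusted. It sits directly after the 13.1.1 list and may describe only how treatment is coded. That is fair: the documents support a finding of silence, not of a deliberately unadjusted design. Carry-over would not settle the matter, though, because for the untreated contrast the dated values are those at diagnosis.

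A reader might infer that 13.1.2 is the only FACE model using switchers' time. The documents do not support that. SAP 3.2 plans category-specific Cox models from the start of each treatment, although 13.4 refers these back to 13.1. The migalastat/ERT model may include previously treated patients, since SAP 12 makes the treatment-naïve comparison a subgroup. The narrower statement, for the composite FACE against untreated, stands.

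A reader might also infer that the drug will appear harmful. Neither document gives progression as the reason for starting or switching. The Primary Effectiveness Population is limited to amenable patients who meet migalastat treatment criteria (SAP 5.2.1). Applied to untreated comparators, that would reduce the confounding. But the criteria are not given, SAP 13.1 also analyses all patients regardless of variant, and eligibility does not equalise when treatment starts. The printed worked example, coded literally, biases the other way.

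Finally, the near-null adjusted results condition on the simulated severity itself. eGFR and LVMi are proxies for it, so real adjustment should be expected to remove less.

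**Conclusion.** The gap is real and should be closed before analysis. As written, 13.1.2 can yield a confounded hazard ratio against untreated, and borrowing the 13.1.1 list would leave most of the bias in the settings simulated.

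The size is conditional. If progression raises both the chance of starting a drug and the FACE hazard to the degree assumed, an inert drug shows a hazard ratio of about 1.2 to 1.7. If starting is unrelated to progression it shows about 1.0. All rates behind these figures are assumptions.

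The false-positive rate does not carry the point: 5 to 8% in simulation B and 5 to 31% in simulation A, so the 31% should not be read as the expected rate. The case rests on bias, where the two simulations agree in direction and rough size. Little bias is expected for migalastat against ERT if that switch is unrelated to progression.

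The worked example is a separate error in the same section. It does not offset the missing covariates.

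**What to change.** In SAP 13.1.2:

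- Make untreated the reference, with two time-dependent indicators (migalastat, ERT), and state the hazard ratios to be reported.
- Adjust for sex, and for age, eGFR and, where available, LVMi valued at or last before the start of each interval.
- Include FACE history before the Analysis Start Date. It cannot update in a first-event model, because a patient leaves at the first FACE.
- Say whether length of treatment is in the model.
- Correct the example so that each event falls in the row of the treatment state in which it occurred.

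In SAP 15.4, state whether the same covariates and timing apply to the time-dependent survival model, and reconcile its example too.

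The cost is SAP wording and programming, on data from the yearly or two-yearly assessments. There are three downsides:

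- **Sparse LVMi.** Echocardiograms are required only where medically necessary (SAP 15.10). The existing rule of dropping a covariate with more than 50% missing can apply.
- **Few events per parameter.** Two indicators and five covariates make seven terms. On the 30 to 36 events of simulation A, that is 30/7 = 4.3 to 36/7 = 5.1 events per term.
- **Values affected by earlier treatment.** Interval-start eGFR and LVMi may already reflect a previous drug, so adjusting for them can remove part of a drug effect. A marginal structural model with inverse-probability weights could be a sensitivity analysis.

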13.2. Secondary Endpoint: Prevalence of FACEs

Treatment Switch

The first analysis will address events that occur on therapy from the Analysis Start Date up until 30 days after the patient stops therapy or from the switch date to the date of a subsequent switch or stopping therapy. The second analysis will address events that occur on therapy from the Analysis Start Date up until the patient stops therapy or switches therapy or from the switch date to the date of a subsequent switch or stopping therapy.

Analysis Method

The prevalence of FACEs is calculated as a ratio of patients with at least one FACE on a given therapy divided by the number of patients on that therapy. If a patient starts dialysis or receives a kidney or heart transplant, the events afterwards will be excluded.

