## **Rationale and background**

Fabry disease is a rare X-linked lysosomal disorder in lysosomes, resulting in a multisystemic disorder caused by deficiency in the enzyme  $\alpha$ -galactosidase A ( $\alpha$ -Gal A) due to mutations in the GLA gene, encoding the hydrolase  $\alpha$ -Gal A enzyme, which catalyses glycosphingolipids namely globotriaosylceramide (Gb3). Reduced or absent  $\alpha$ -Gal A activity leads to accumulation of Gb3 in the lysosomes of various organs, as well as cellular dysfunction and inflammation causing physical symptoms and eventual organ failure (1,2). Fabry disease as an X-linked disorder with a high penetrance, though not 100% in female heterozygotes, although the disease affects both males and females. With the X-linked nature, Fabry disease is suitable for an efficient, high diagnostic yield cascade screening over at least three generations surrounding an index-patient. The Danish National Fabry Centre has now more than 20 years of experience of cascade screening, which has provided a patient population of 115 male and female patients. The prevalence of Fabry disease in the Danish population is estimated to be 1:58000 (males 1:85000, females 1:44000) (3).

Primarily male patients, with early onset classical phenotypes have none or very low  $\alpha$ -Gal A activity, and they inevitably develop multiorgan failure without treatment (4). Patients with late onset of Fabry disease represent both males and females with higher  $\alpha$ -Gal A activity and variable degrees of organ involvement (5). Fabry disease can cause irreversible damage to multiple organs resulting in Fabry associated clinical events (FACEs) such as renal, cardiac, cerebrovascular events, and death (5).

The primary Fabry specific therapy has historically been enzyme replacement therapy (ERT), and as of 2016 an oral chaperone therapy, Migalastat, has been available, providing an alternative to ERT for patients with amenable mutations by increasing their endogenous  $\alpha$ -Gal A enzyme activity (6–14). However, real-world long-term data from well-characterised cohorts with available detailed clinical consecutive observations with focus on treatment with Migalastat and Fabry associated events has not been fully investigated (12–14).

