## **Secondary endpoints**

### **The secondary endpoints**

- The prevalence of FACEs from each baseline (diagnosis, and start of treatment) to compare between Migalastat-treated, ERT-treated patients and non-treated patients
- The incidence of FACEs from each baseline (diagnosis, and start of treatment) to compare between Migalastat-treated, ERT-treated patients and non-treated patients

- Time to the first cardiac, cerebrovascular, and renal clinical event separately by each specific category (including death in these categories) from start of treatment or baseline
- Incidence of cardiac, cerebrovascular, and renal clinical events separately by each specific category (including death in these categories)
- Occurrence of cardiac, cerebrovascular, and renal clinical events separately by each specific category (including death in these categories)
- Annualized rate of change in eGFR based on the Chronic Kidney Disease Epidemiology Collaboration equation (eGFRCKD-EPI) over time to compare between Migalastat-treated, ERT, and untreated patients
- The prevalence and incidence of a clinically significant change in mGFR and/or eGFR (according to KDIGO guidelines rapid progression is defined as a sustained decline in eGFR of more than 5 ml/min/1.73 m^2 /yr) from each baseline (diagnosis, and start of treatment) to compare between Migalastat-treated, ERT-treated patients and non-treated pts
- The prevalence and incidence of micro (> 30 mg/g creatinine) or macroalbuminuria (> 300) by urinary albumin/creatinine ratio (ACR) or urinary 24 h protein excretion from each baseline (diagnosis, and start of treatment) to compare between Migalastat-treated, ERT-treated patients and non-treated pts

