## Study workflow

Fabry patients entered the study at their baseline visit (first visit in the center) from 2001 with last follow-up December 2022. Patient data will be grouped for the whole duration of the defined study period, with individual datapoints registered at the specific date of event/measurement. Ideally the datapoints will be used according to their specific dates but may be aggregated according to availability. Details is further described in the statistical analysis plan.

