2. OVERVIEW OF STUDY DESIGN

This is a retrospective study of prospectively collected patient data with the use of secondary patient data from both paper and electronic patient files. All patients are treatment naïve at time of diagnosis. Both migalastat and ERT will be studied retrospectively. Also untreated patients will be studied by assessment of relevant clinical and laboratory variables. The analysis will originate at the time of diagnosis.

The patients have been followed for more than 20 years from 2001 until December 2023. All identified patients with Fabry disease, whether receiving specific Fabry medication or not, have been offered annual or biannual thorough workups including examinations of Fabry associated organ function and symptoms. The study will be carried out at the Danish National Fabry Centre, Department of Endocrinology, Copenhagen University Hospital.

All patients from the Danish National Fabry Centre will be included. Subgrouping is aimed at depending on available numbers: non-amenable, amenable, classic, non-classic, males, females, treated including type of treatment or untreated.

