13.9. Secondary Endpoint: Prevalence and Incidence of micro – or Macroalbuminuria

The prevalence and incidence of micro (> 30 mg/g creatinine) or macroalbuminuria (> 300) by urinary albumin/creatinine ratio (ACR) or urinary 24 h protein excretion from each baseline (diagnosis, and start of treatment) to compare between migalastat-treated, ERT-treated patients and untreated patients will be analyzed using same methodology as for incidence and prevalence of FACEs.

Analysis by ACR categories will be performed if enough data are available.

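### FACE prevalence in SAP 13.2 is a crude proportion with no time at risk, so comparing it between treatments mixes any drug effect with length of observation

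*SAP*

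**What the plan says.** **Definition.** SAP 13.2 defines prevalence as the "ratio of patients with at least one FACE on a given therapy divided by the number of patients on that therapy". Two on-therapy windows are given, one with a 30-day extension after stopping and one without. For the latter: "The second analysis will address events that occur on therapy from the Analysis Start Date up until the patient stops therapy or switches therapy". Both follow the patient's own treatment period, so their length varies by patient and by therapy.

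**Purpose.** The Protocol's secondary endpoints include "The prevalence of FACEs from each baseline (diagnosis, and start of treatment) to compare between Migalastat-treated, ERT-treated patients and non-treated patients". SAP 3.2 gives the significance level for everything beyond the primary comparison: "All other comparisons will also be done at the 2-sided significance level of 0.05 with no adjustment for multiple comparisons". SAP 17.1 declares no changes from the Protocol.

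**Dates.** The Protocol's background says that "as of 2016 an oral chaperone therapy, Migalastat, has been available". Its study workflow says "Fabry patients entered the study at their baseline visit (first visit in the center) from 2001 with last follow-up December 2022". SAP section 2 gives a later end: "The patients have been followed for more than 20 years from 2001 until December 2023".

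**Reach.** SAP 13.9 analyses albuminuria "using same methodology as for incidence and prevalence of FACEs", and 13.8 does likewise for decline in GFR. SAP 13.5 (incidence by category) refers to 13.2, and 13.6 (prevalence by category) refers to 13.3. These two references appear to be swapped.

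**The concern.** A proportion with at least one event grows with the time over which events can be counted. If one group is observed on therapy for a few years and another for a decade or more, the proportions differ even when the yearly risk is the same. Here the calendar limits migalastat exposure and does not limit untreated exposure in the same way. The Protocol describes ERT as the historical mainstay but gives no date for it.

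At stake is a listed secondary comparison in a study whose stated focus is the added value of migalastat. A lower FACE prevalence on migalastat could be read as benefit when it reflects only shorter observation. Nothing in the SAP labels the proportion as descriptive, asks for exposure to be shown beside it, or ties its reading to the person-year rates in 13.3.

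**Working it through.** The plan states no expected prevalence, event rate or time on therapy, so there is no figure to reproduce. The check asks what the 13.2 measure returns when the groups truly do not differ.

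**1. Exposure ceilings, from the documents (calendar years counted inclusively).**
- Migalastat: 2016 to end 2022 is 2022 − 2016 + 1 = 7 years; to end 2023 it is 8 years.
- Study window: 2001 to end 2022 is 2022 − 2001 + 1 = 22 years; to end 2023 it is 23 years.

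**2. Model (assumption).** The first-event hazard h is constant and the same in both groups. Expected proportion after t years on therapy: p(t) = 1 − exp(−h·t). The true ratio is 1.0.

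**3. Illustrative exposures.** Hazards of 0.02 to 0.05 per year and 3 to 4 against 10 to 15 years are assumptions. Worked example, h = 0.03: p(4) = 1 − exp(−0.12) = 11.3%; p(10) = 1 − exp(−0.30) = 25.9%; ratio 0.44. Corners of the grid:

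| Years, migalastat vs comparator | h = 0.02 | h = 0.05 |
|---|---|---|
| 3 vs 10 | 5.8% / 18.1% = 0.32 | 13.9% / 39.3% = 0.35 |
| 4 vs 10 | 7.7% / 18.1% = 0.42 | 18.1% / 39.3% = 0.46 |
| 3 vs 15 | 5.8% / 25.9% = 0.22 | 13.9% / 52.8% = 0.26 |
| 4 vs 15 | 7.7% / 25.9% = 0.30 | 18.1% / 52.8% = 0.34 |

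The false ratio runs from 0.22 to 0.46.

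**4. Exposures at or spread up to the ceilings.** With fixed times of 7 vs 22 years and h from 0.01 to 0.06, the ratio is 0.34 to 0.47 (8 vs 23 years: 0.37 to 0.51). With durations uniform on 0–7 and 0–22 years, the expected proportion is 1 − [1 − exp(−hT)]/(hT), where T is the upper limit. At h = 0.02 this gives 6.7% vs 19.1% (0.35); at h = 0.04, 12.8% vs 33.5% (0.38).

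**5. If the proportions were tested.** SAP 13.2 names no test, so Fisher's test stands in. In 3,000 simulated datasets per scenario (uniform durations as in step 4, groups of 20 vs 40 and 30 vs 50, h = 0.02 to 0.06, no true difference), it rejected at 0.05 in 17% to 67%. An exact test on person-time rates rejected in 2.6% to 4.1%. Group sizes are assumptions.

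**6. When the direction fails.** Let a fraction of untreated periods end after 0.25 to 2 years and the rest be uniform on 0–22 years, with migalastat uniform on 0–7. Ratios at h = 0.02 and 0.04:
- 50% leaving early: 0.63 and 0.67
- 70%: 0.92 and 0.97
- 75%: 1.04 and 1.10
- 80%: 1.19 and 1.25

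**7. The alternative measure.** Cumulative incidence at a common 5 years is 9.5% in both groups at h = 0.02 and 18.1% in both at h = 0.04. The ratio is 1.0, as it should be.

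**The case against.** **The plan already handles time elsewhere.** The primary Cox model (13.1.1), the log-rank sensitivity analysis, the interval-based Cox model (13.1.2) and the rates per 1000 person-years (13.3) all use time at risk. This stands. A reader might infer that the primary conclusion is compromised by this defect, and it is not. But prevalence is a separately listed comparison, and a sound companion analysis does not make it valid.

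**No test of prevalence is specified.** Also correct. SAP 13.2 gives only a ratio, and the FACE prevalence bullet in SAP 3.2 drops the Protocol's wording about comparing. A reader might infer from the general 0.05 statement that a test of these proportions is planned, but that statement only sets a level for whatever comparisons are made. On the other side, the lead-in to SAP 3.2 sets migalastat against untreated or ERT patients, 13.8 and 13.9 keep comparative wording, and no change from the Protocol is declared. The text is ambiguous, and an untested side-by-side comparison would mislead in the same way.

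**The direction is not fixed.** A reader might infer that the measure favours the sponsor's drug by construction. The documents do not support that. The 2016 date caps migalastat time but says nothing about actual time on any therapy. All patients are treatment naive at diagnosis, and only those treated within 3 months are reassigned (SAP 5.1 and 5.2.1). The untreated group may therefore hold many short periods, and step 6 shows the bias vanishing or reversing if most are short.

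**Reach.** It would be wrong to say simply that 13.6 inherits the measure. As written, 13.6 points to the person-year section and 13.5 points to the crude proportion.

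**Conclusion.** The concern holds in this form. The prevalence measure in SAP 13.2 cannot separate a treatment effect from length of observation, and the documents' own dates allow very unequal observation: at most about 7 to 8 years on migalastat within a window of 22 to 23 years.

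Under equal hazards the comparison is expected to favour migalastat, with a false ratio of about 0.22 to 0.46 for the assumed hazards (0.02 to 0.05 per year) and exposures (3 to 4 against 10 to 15 years). These figures illustrate the size and do not estimate it for this cohort. The direction holds only if time on migalastat is typically shorter than on the comparator.

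The defect covers 13.2, the prevalence parts of 13.8 and 13.9, and either 13.6 (as titled) or 13.5 (as literally referenced). It should be corrected before analysis.

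**What to change.** 1. **SAP 13.2.** Make the between-group comparison on cumulative incidence of first FACE at fixed horizons reachable on migalastat, for example 2 and 5 years from the start of the treatment period, with non-FACE death as a competing event. Alternatively, rest the comparison on the 13.3 rates. In that case choose one numerator, since 13.3 refers both to patients with at least one event and to number of events.
2. **Crude proportion.** Keep it only as a clearly labelled descriptive figure, with person-years and median time on therapy per group and no between-group test.
3. **Cross-references.** Point 13.5 to 13.3, and 13.6 to the amended 13.2.
4. **SAP 13.8 and 13.9.** Apply the descriptive-only rule to the crude proportion. Use time-based estimates only for new-onset events in patients free of the condition at period start. Albuminuria may already be present then, and rapid GFR decline is defined by a yearly rate, so its onset date needs a rule.
5. **Clock start.** Reconcile SAP 3.1, which counts migalastat from start of treatment, with SAP 11.2, which uses diagnosis for the comparison with untreated patients, because this sets the window.

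**Cost.** SAP wording and one further standard estimate from data already being collected. Later horizons will not be estimable for migalastat. Complete 5-year follow-up is possible only for patients who started by end 2017 (2022 − 5) or end 2018 (2023 − 5).
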